2.1 Study Aims and Objectives

• To test our hypothesis that usual care in addition to either standardised cognitive behavioural approach (CBA) or personalised exercise programme (PEP) interventions is more effective than usual care alone to lessen the impact and severity of fatigue after 56 weeks from baseline. Please see the protocol for the primary here and then add secondary hypotheses/research questions.

2.2 Study Design

• The LIFT study is a multi-centre, three-arm pragmatic randomised controlled trial testing usual care alone versus usual care with additional adapted CBA or PEP therapies, figure 1

2.3 Interventions to be evaluated (All arms are fully defined in the protocol)

- Usual care: Arthritis Research UK's information booklet¹⁸ for self-management of fatigue represents usual care in almost all UK rheumatology centres and is freely available. It covers the major relevant topics underpinned by goal-setting and self-monitoring of activity. It encourages that patients ask for support to work through the booklet.
- Both active interventions will last 14 weeks with a booster at 22 weeks. (protocol section 4.1 and figure 2)
- The *Cognitive behavioural approach (CBA)* is a structured psychological intervention, aiming to replace unhelpful beliefs and behaviours with more adaptive ones. It will use patient-centred strategies and behavioural activities, supported by written materials and regular consultations with rheumatology health care professionals. Participants will receive additional leaflets and diaries about making changes to manage fatigue. The times and duration of keeping the diary as well as the exchange of content will be set individually for each patient in collaboration with the allocated therapist.

• The *Personalised Exercise Programme (PEP)* is theoretically based on the premise that chronic fatigue relates to physical activity (PA) intolerance, supported by unhelpful illness beliefs and deconditioning, thus increased perception of effort. PEP aims to disrupt this cycle with graded exposure to behaviour therapy contingent on symptoms, to gradually optimise patients levels of PA so as to modify altered perceptions of effort, improve tolerance of PA, fitness and function, reverse the deconditioning and ultimately reduce the severity and impact of fatigue. Participants will receive a tailored graded exercise programme, initially delivered according to physical capacity, gradually increasing in duration and intensity. Participants will receive additional information and diaries. The times and duration of keeping the diary as well as the exchange of content will be set individually for each patient in collaboration with the allocated therapist. The intervention will utilise pedometers and/or heart rate monitors for goal-setting and to enhance motivation.

3 Randomisation, Allocation and Blinding

After consent, participants will be randomised via Centre for Healthcare Randomised Trials (CHaRT) based within the University of Aberdeen. The CHaRT provides a 24 h randomisation web-based service. Using a computer-generated sequence, participants will be allocated to one of the two treatments or usual care (1:1:1 ratio).

Randomisation will be minimised by diagnosis (Rheumatic Arthritis [RA], Systemic Lupus Erythematosus [SLE], Axial Spondyloarthritis [AxSpA] or other Inflammatory Rheumatic Disease [IRD]) and the presence/absence of depressive symptoms (Hospital Anxiety & Depression Scale (HADS-D) depression subscale >10⁹ and will include a random element set at 20%. That is, 20% of all the allocated randomisations will be randomly re-allocated 50:50 to the remaining two treatment options.

Full blinding will not be possible due to the need to engage people in behavioural change. However, we will aim to blind research personnel undertaking outcome assessments to participants' treatment allocation – including the trial statistician with the data being analysed blind to allocation, until the final analyses.

4 Data Monitoring

While there are no planned interim analyses for efficacy or futility, an independent Data Monitoring Committee (DMC) will monitor trial progress and specifically any safety issues. The data available at each DMC will be preserved, along with all documentation of analysis plans, programming code and reporting provided.

For this relatively simple design, the biases should be minimal with the biggest threat being due to data missingness. However, to minimise bias:

- Only the DMC will see any data or analyses for their decisions making, prepared by the trial statistician (blinded –a colleague will re-run the code to reveal the true allocations for each interim report)
- The trial statistician will perform the final analyses, remaining blinded until the final follow-up and data entry has been completed

5 Timing of final Analyses

The final analyses will be performed after the last participants' final follow-up information has been collected and data entered.

6 Timing of Outcome Measurements

The outcome measurements have been planned be taken within a one-week period at defined times (10, 28 and 56 weeks) post randomisation. The actual times will be summarised in the results.

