# 6.2 Blinding

Full blinding will not be possible due to the need to engage people in behavioural change. However, to reduce detection bias, we will aim to blind research personnel undertaking outcome assessments to participants' treatment allocation. To facilitate blinding we will remind participants to refrain from discussing (and subsequently revealing) their treatment allocation at follow-up assessments with the research personnel. Finally, data will be analysed blind to allocation.

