#### 10.2 Proposed Analysis

All statistical analyses will be governed by a comprehensive Statistical Analysis Plan, which will be authored by the study statistician and approved by the Trial Steering Committee and the Data Monitoring Committee before the main study outcome data are examined. All analyses will be carried out using Stata. In accordance with CONSORT guidelines, we will report all participant flow. Descriptive statistics of recruitment, drop-out and completeness of interventions will be provided.

Effectiveness Analysis: The main effectiveness analysis will be via intention-to-treat including all participants, with no planned interim analysis for early termination for either overwhelming evidence of effectiveness or abandoning for futility. Baseline characteristics will be presented by randomised group without formal statistical tests. We will test the primary hypothesis for between-group change in the primary outcome for each of the two pre-specified comparisons (CBA + usual care vs usual care alone and PEP + usual care vs usual care alone) using repeated measures mixed model, with subject as a random effect, and a suitably specified covariance structure (e.g. Autoregressive [1] (AR[1]), rheumatology healthcare professional as a random effect (to adjust for any clustering by rheumatology healthcare professional), with baseline outcome measure, and any other strongly predictive baseline measures, including the minimisation factors of presence/absence of depression and centre, and diagnosis. Treatment and its interaction with time will be fitted as fixed effects, and we apply standard regression diagnostics. The analysis will use statistical techniques for handling missing outcome data using multiple imputation under a missing at random (MAR) assumption. The secondary outcomes will be analysed using an analogous method. The main estimate of treatment effect will focus on the 56 weeks after baseline.

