11.8 COVID-19

The effect of COVD-19 will be explored. In the first instance, periods before, during and after COVID-19 will be summarised using appropriate descriptive statistics and graphical summaries. If need be, formal analysis will be carried out to explore the effect of COVID-19, that may include time of recruitment in relation to UK lock-down (23rd March 2020) and local conditions at the time each outcome is measured. Attempts will be made to account/adjust for the multiple lockdowns and variations of that around the country using emerging methodologies.

12 Technical Details

Protocol version (vs 11) will be consulted for this SAP. All statistical analyses will use stata (vs 15 for DMC's – and vs 16 for the final analyses). All results will be processed directly into PDF/Word from Stata via LaTEX (MiKTeX 2.9 at time of writing) for the DMC's, the use of putdocx commands in Stata 16 for the final Statistical Report.

13 Dummy Tables

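### The protocol promises analysis blind to allocation, but the SAP lets the trial statistician be unblinded before the final analyses while some choices are still open

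*SAP*

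**What the plan says.** Protocol 6.2 accepts that participants cannot be fully blinded. It then lists what will be done instead, ending with "Finally, data will be analysed blind to allocation". No exception or end point is given.

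SAP 3 repeats the undertaking for staff, "including the trial statistician with the data being analysed blind to allocation, until the final analyses". SAP 4, in its list of measures against bias, states: "The trial statistician will perform the final analyses, remaining blinded until the final follow-up and data entry has been completed". SAP 5 adds: "The final analyses will be performed after the last participants' final follow-up information has been collected and data entered".

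For DMC reports the SAP has a different arrangement. The statistician prepares them blinded, and "a colleague will re-run the code to reveal the true allocations for each interim report".

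Protocol 10.2 requires the SAP to be "approved by the Trial Steering Committee and the Data Monitoring Committee before the main study outcome data are examined".

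**The concern.** Participants know their treatment, and both primary outcomes (CF and FSS) are self-completed questionnaires. Few protections against bias are available in such a trial, and blind analysis is one that the protocol names. If the analyst may know the arms before the final models are fitted, any modelling decision still open at that point can be influenced, even unintentionally, by which arm it favours. The trial would also be unable to report accurately that its analysis was blind, because following SAP 4 does not guarantee what protocol 6.2 states.

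**Working it through.** The point is mainly one of text. The sample size does not depend on when the analyst is unblinded.

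**Step 1: order of events.**

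| Source | When blinding of the analysis ends |
|---|---|
| Protocol 6.2 | No end stated |
| SAP 3 | At the final analyses |
| SAP 4 | When final follow-up and data entry are complete |
| SAP 5 | (Final analyses are run after follow-up and data entry are complete) |

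SAP 4 and SAP 5 together give this sequence: data entry complete, unblinding permitted, final analyses by the same person. The SAP names no database lock, blind data review or sign-off of open choices between the first and third steps.

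**Step 2: what is already fixed.** The following are written down in advance:
- the two comparisons with usual care, and 56 weeks as the primary time point (SAP 6.1, 11.2.1);
- adjustment for baseline outcome, diagnosis and depressive symptoms (SAP 11.2);
- available data as the basis of the primary estimate, and a trigger of more than 10% missing for further sensitivity work (SAP 11.5);
- item-level missing-data rules, decided on 21/06/2019 (SAP 11.7 and appendix).

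**Step 3: what is still open and bears on CF, FSS or their sensitivity set.**
1. *Covariance structure.* Protocol 10.2 leaves it to be suitably chosen, with AR(1) as an example. SAP 11.2 and the Table 8 footnote give random effects for centre and individual but name no residual structure.
2. *Regression diagnostics.* SAP 11.2.1 says they will be applied but not what follows if they are unsatisfactory.
3. *Missing-data method.* Above the trigger, SAP 11.5 allows multiple imputation, missing-not-at-random models, or both. Protocol 5.1 plans for 125 recruited and 100 evaluable per group, so (125 − 100)/125 = 20% missing at 56 weeks. That exceeds 10%, so on the plan's own assumption this choice will have to be made.
4. *COVID-19.* SAP 11.8 says "If need be, formal analysis will be carried out to explore the effect of COVID-19", and leaves the method of adjustment to emerging methodology.

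Items 1 and 2 touch the primary model itself. Items 3 and 4 touch the supporting analyses.

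**Step 4: what does not count.**
- *Link function:* SAP 11.2 leaves it to depend on the outcome, but Table 8 reports mean differences on continuous scores for CF and FSS, so it is effectively settled for them.
- *Moderators:* the list is blank in SAP 11.3, but the analysis is exploratory and belongs to a secondary phase.
- *CACE (complier average causal effect):* it is a sensitivity analysis whose adherence variable and substitution rule are stated. Only whether to run it is open. It relies on therapist-reported adherence, which identifies the active arms, so it could not be done blind anyway.

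**The case against.** The best case against the point has three parts.

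First, protocol 10.2 makes the SAP the governing document for analysis, so SAP 3 and 4 can be read as refining a one-line protocol statement. That explains the difference but does not remove it: protocol 6.2 is still unqualified, and a reader of the protocol would expect a blind main analysis.

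Second, the SAP must be approved by two committees before the main outcome data are examined, and much is pre-set (step 2). This stands as a real protection. However, approval fixes only what is written, and the four items in step 3 are not.

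Third, blind final analysis is not the only remedy. Amending protocol 6.2 and dating the finalisation of the SAP before unblinding would also make the documents agree. This also stands, and appears below as the fallback.

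Two stronger readings are tempting and should be resisted. A reader might infer that the open choices *are* made knowing the arms. The documents do not say so: SAP 4 states when blinding may end, and no section says when modelling choices are taken. A reader might also infer that every unfinished item in the SAP can move the 56-week contrast. Step 4 shows otherwise, and the COVID-19 work is descriptive in the first instance and is not stated to replace the primary model.

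**Conclusion.** The concern holds in a limited form. Protocol and SAP conflict on whether the main analysis is blind, and as written the SAP does not deliver the safeguard. Four choices are exposed: two in the primary model and two in its sensitivity set. No effect on the estimate is shown, and none can be calculated. The risk is reduced, but not removed, by prior approval of the SAP and its pre-set rules. It merits correction before unblinding because the trial is open-label with self-reported primary outcomes and the remedy is cheap.

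This rests on two assumptions: that the final analyses in SAP 3 to 5 mean the main 56-week effectiveness analysis, and that where the protocol and SAP differ on analysis detail, the SAP is followed.

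**What to change.** Change SAP 3 and 4 as follows:

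- The trial statistician develops the primary CF analysis, the FSS analysis, and the missing-data and COVID-19 sensitivity analyses on masked arm codes, with adherence and therapist data withheld.
- Because both primary comparisons are against usual care, the masked code produces all three pairwise contrasts or uses a masked reference arm. With treatment and its interaction with time in the model, the choice of reference arm only relabels the coefficients, so model checking is unaffected.
- Before unmasking, the database is locked, the remaining choices (covariance structure, response to diagnostics, missing-data method, COVID-19 adjustment) are recorded and dated, and the code is locked.
- A colleague then applies the true allocation and re-runs the locked code.
- CACE, therapist-level, adherence, mediation and moderation analyses are exempt and follow unmasking.

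The cost is SAP wording plus a small amount of extra programming and sign-off. The colleague re-run already exists for DMC reports, although extending it to final modelling is some additional work.

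If the sponsor does not adopt this, protocol 6.2 must be amended to say that the final analysis is not blind, and the trial report must not claim that it was. In that case a dated finalisation of the open choices before unblinding would still be worth having.

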6.1 Primary Outcomes (Specifically at 56 weeks)

- Chalder Fatigue Scale (CF)¹⁶ assessing the physical and mental symptoms of fatigue as a total score using the Likert scale version and not as sub-domains
- Fatigue Severity Scale (FSS)¹⁷ assessing the impact of fatigue.

If the effect of intervention is positive on the CF, then the FSS outcome will be formally analysed. Should the intervention have no effect on the CF, then an explorative analysis of the FSS outcome will be performed.

(prior to 56 weeks these are also monitored and will be included in the final model but are considered as secondary outcomes)

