# 3.1 **Primary Outcome**

The primary outcome fatigue is determined with the Chalder Fatigue Scale (CF) [31] using the Likert scoring, assessing the physical and mental symptoms of fatigue, and the Fatigue Severity Scale (FSS) [32] assessing the impact of fatigue after 56 weeks. If the effect of intervention is positive on the CF, then the FSS outcome will be formally analysed. Should the intervention have no effect on the CF, then an explorative analysis of the FSS outcome will be performed (details see 10.2).

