# **10 STATISTICS AND DATA ANALYSIS**

#### **10.1 Sample Size Calculation**

Our planned primary intention to treat analyses will compare PEP + usual care versus usual care alone, and CBA + usual care versus usual care alone separately. We base our calculations on a standardised effect size of 0.50 (considered credible in other pragmatic effectiveness studies), which would equate to being powered to detect a minimal important clinical difference of 2 units in the CF Scale, assuming a common standard deviation across the randomised groups of 4 units. Assuming an overall significance level of 5% (by calculating the two pre-specified randomised groups comparisons, PEP + usual care vs. usual care alone and CBA + usual care vs usual care alone, at 2.5%, to maintain an overall level of not more than 5%) and a power of 90%, we require 100 evaluable participants in each of the three groups.

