Our planned primary Intention-to-Treat analyses (ITT) will compare PEP + usual care versus usual care alone, and CBA + usual care versus usual care alone. This was based on a standardised effect size of 0.50 (considered credible in other pragmatic effectiveness studies), which would equate to being powered to detect a minimal important clinical difference of 2 units in the CF Scale, assuming a common standard deviation across the randomised groups of 4 units, as with PACE ¹⁹. Assuming an overall significance level of 5% (by calculating the two pre-specified randomised groups comparisons, PEP + usual care vs. usual care alone and CBA + usual care vs usual care alone, at 2.5%, to maintain an overall level of not more than 5%) and a power of 90%, we require 100 evaluable participants in each of the three groups.

11 Statistical Methods

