11.1 General Methods

All the main analyses will be based on the ITT principle and utilise all available follow-up data from all randomised participants who provide consent. Any post-randomisation exclusions will be removed. Final analysis will take place after full recruitment and follow-up. The results of the trial will follow the guidelines of the CONSORT statement developed specifically for social and psychological intervention trials ³ when presenting and analysing the data. Baseline characteristics of the study population will be summarised separately using the appropriate descriptive statistics and graphical summaries within each randomised group. Baseline characteristics will also be presented for dropouts and completers within each intervention group.

Treatment effects will be tested at the 2-sided 5% significance level with any estimates displayed with 95% confidence intervals (CIs) and p-values. There will be no

SAP version 1: LIFT

adjustment to secondary outcomes CIs for multiple testing. (See section 3 for statistician blinding)

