11.2 Statistical Analysis

LIFT has repeated measures on individual participants nested within site suggesting a multilevel model with an appropriate link function depending on the outcome. The analysis will adjust for the outcome variable at baseline as a covariate (when available) as well as the design factors also at baseline [diagnosis (RA, SLE, AxSpA or other IRD), the presence/absence of depressive symptoms HADS depression subscale >10)]. Centre clustering will be accounted for using a random effects robust variance.

11.2.1 Primary Outcome - Effectiveness Analysis.

We will test the primary hypothesis for between-group change in the primary outcome for each of the two pre-specified comparisons (CBA + usual care vs usual care alone and PEP + usual care vs usual care alone) using treatment and its interaction with time fitted as fixed effects, and we apply standard regression diagnostics. The main analysis will focus on the 56 weeks after baseline – providing effect sizes for each of the active arms compared to usual care. Standard regression diagnostics will be applied.

A Complier Average Causal Effect (CACE) analysis will be considered as a sensitivity analysis. Patent engagement & adherence (therapist view) at 8 weeks forms the CACE variable (if missing the 4 weeks reported value will be substituted) as a continuous instrumental variable in the CACE analysis

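### The rule that makes FSS a formal primary test names no arm, criterion or FSS level, so the promised overall 5% holds on one reading and not on another

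*SAP*

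**What the plan says.** Protocol 3.1 and SAP 6.1 both name CF and FSS at 56 weeks as primary outcomes. The SAP sets the order of testing: "If the effect of intervention is positive on the CF, then the FSS outcome will be formally analysed". Protocol 3.1 gives the other branch and a cross-reference: "Should the intervention have no effect on the CF, then an explorative analysis of the FSS outcome will be performed (details see 10.2". The notes to SAP Table 8 repeat the rule. Protocol 10.2, to which the reader is sent, mentions neither FSS nor the gate.

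The primary hypothesis is tested "for each of the two pre-specified comparisons (CBA + usual care vs usual care alone and PEP + usual care vs usual care alone" (SAP 11.2.1; protocol 10.2 is equivalent). SAP section 10 and protocol 10.1 protect the error rate by dividing it between those two comparisons, "at 2.5%, to maintain an overall level of not more than 5%) and a power of 90%, we require 100 evaluable participants" per group. FSS has no part in that division.

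SAP 11.1 sets a different general level: "Treatment effects will be tested at the 2-sided 5% significance level with any estimates displayed with 95% confidence intervals (CIs) and p-values".

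**The concern.** Two therapies and two primary outcomes make four possible primary tests. The 2.5% split accounts for two of them. The FSS tests are protected only by the gate, and the gate leaves three things open.

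- **Which arm.** It speaks of a single intervention in a trial with two. If CBA succeeds on CF and PEP does not, the text does not settle whether PEP's FSS result is formal or exploratory.
- **What opens it.** Positive is given neither a direction nor a significance level.
- **FSS level.** Nothing specific is stated, so the 5% of SAP 11.1 applies by default.

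One therapy succeeding on CF while the other fails is a realistic outcome when two different therapies are tested. If the reading is not fixed beforehand, it can be chosen after the CF results are known. At stake are the overall error rate and whether a therapy that missed on CF may still claim a formal primary result on FSS.

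**Working it through.** **Inputs from the documents.** Difference 2 CF units, SD 4, 2.5% per comparison, 90% power, 100 evaluable per group (protocol 10.1, SAP section 10); 1:1:1 allocation (SAP section 3); 20% dropout, 125 recruited per group (protocol 5.1).

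**Assumptions.** Equal groups sharing one control give a correlation of 0.5 between the CBA and PEP comparisons. The documents give no CF-FSS correlation r, so 0 to 0.9 is shown. The correlation between CF for one therapy and FSS for the other is taken as 0.5r.

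**Step 1: the plan's own figures.** n = 2(z₀.₉₈₇₅ + z₀.₉₀)² / 0.5² = 2(2.241 + 1.282)² / 0.25 = 99.3, so 100 per group. 100 / 0.80 = 125. Two comparisons: 2.5% + 2.5% = 5%. The stated numbers reproduce with two-sided 2.5% tests and count no FSS test.

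**Step 2: gate applied per therapy, every test at 2.5%.** If a therapy has no CF effect, any false rejection in that arm first needs a false CF rejection: at most 2.5%. If it does have a CF effect, only FSS can be falsely rejected: again at most 2.5%. Two arms give at most 2.5% + 2.5% = 5%, whatever r is.

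**Step 3: one gate shared by both therapies, every test at 2.5%.** Suppose CBA works on CF only and PEP on neither outcome. Once CBA's CF result opens the gate, three true null hypotheses are tested: CBA on FSS, PEP on CF, PEP on FSS. The ceiling is 3 × 2.5% = 7.5% (1 − 0.975³ = 7.3% if independent).

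Four correlated z statistics were simulated, with CBA's CF mean at the planned effect, 2 / (4√(2/100)) = 3.54 (90.2% power), or so large that success is near certain. Overall two-sided error, repeatable to about 0.1 percentage point:

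| CF-FSS correlation | Shared, planned power | Shared, near-certain power | Per therapy, planned power | Per therapy, near-certain power |
|---|---|---|---|---|
| 0 | 6.6% | 7.0% | 4.7% | 4.9% |
| 0.3 | 6.4% | 6.9% | 4.5% | 4.9% |
| 0.5 | 6.0% | 6.7% | 4.3% | 4.9% |
| 0.7 | 5.3% | 6.4% | 4.0% | 4.8% |
| 0.9 | 4.5% | 5.7% | 3.7% | 4.7% |

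Requiring the CF result to favour therapy before the gate opens leaves these figures essentially unchanged, so defining the direction alone does not help.

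**Step 4: other true states, shared gate at 2.5%.** No effect anywhere: about 4.6%. Both therapies work on CF, neither on FSS: about 4.6%. CBA works on both outcomes and PEP on neither: at most 2 × 2.5% = 5%.

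**Step 5: false claims of benefit only.** In the step 3 scenario, the shared gate gives at most about 3.5% (ceiling 3 × 1.25% = 3.75%). If CBA works on both outcomes, an ineffective PEP obtains a false formal benefit about 2.1% to 2.4% of the time for r of 0.3 to 0.7, against 1.25% with a per-therapy gate.

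**Step 6: every test at the 5% of SAP 11.1.** In the step 3 scenario a per-therapy gate gives about 7.5% to 9.8% (ceiling 5% + 5% = 10%). A shared gate gives 10.9% to 13.6% at near-certain power (ceiling 15%).

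**The case against.** The best defence is that the gate is naturally read per therapy. The protocol summary says the interventions are tested individually, protocol 10.1 says the comparisons are made separately, and protocol 10.2 and SAP 11.2.1 test the hypothesis for each comparison. The closed branch, "Should the intervention have no effect on the CF, then an explorative analysis of the FSS outcome will be performed", applied to PEP alone would make PEP's FSS result exploratory. On that reading, at 2.5% per test, the 5% promise holds.

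Much of this stands. A reader might infer that the plan lets CBA's success open FSS for PEP. No passage says so; it is one reading of unclear text. A reader might also infer that the overall level fails in general. It does not: step 4 shows no breach in the other states examined, and at planned power with correlation 0.9 there is none even in the step 3 scenario. Nor do the results support saying that an ineffective therapy wins a formal success 4% to 5% of the time; that counts two-sided rejections, about half of which favour usual care. The absence of a formal or exploratory label in Table 8 proves little, because it is a dummy layout with the rule restated beneath it.

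What the defence does not supply is the missing specification. The passages on separate comparisons describe the comparisons, not the gate. The cross-reference to protocol 10.2 leads to no details. A per-therapy reading also leaves positive undefined and FSS at 5%.

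**Conclusion.** The point holds as a gap in specification, not as a demonstrated error in the testing rule. The documents do not secure an overall level of at most 5% across the four primary tests, because that depends on a reading of the gate and a test level that they do not fix.

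The excess from a shared gate is modest: about 5.3% to 6.4% at planned power and 6.4% to 6.9% at near-certain power, for correlations of 0.3 to 0.7. It needs one therapy to affect CF but not FSS while the other affects neither. It refers to two-sided error, which is the SAP's convention, and rests on an assumed CF-FSS correlation.

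The 5% level in SAP 11.1 is the larger contributor: if it governs the primary tests, the promise fails even with a per-therapy gate. The two matters are separate, since moving every test to 2.5% does not settle which arm the gate refers to. Both should be resolved before allocation is revealed.

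**What to change.** In SAP 6.1, protocol 3.1 and the Table 8 notes, replace the gate with:

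*For each therapy separately, FSS at 56 weeks is tested formally at two-sided 2.5% only if that therapy's CF effect at 56 weeks favours the therapy at two-sided 2.5%; otherwise its FSS result is labelled exploratory.*

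Amend SAP 11.1 so that these primary tests use two-sided 2.5%, label FSS results in Table 8 as formal or exploratory, and correct the cross-reference to protocol 10.2.

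The cost is a few lines of text. It needs no extra data, and 100 evaluable participants per group still suffices for CF. The one loss is that a therapy failing on CF can make no formal FSS claim. If a per-therapy gate was always intended, the sentence simply records it.
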